7.3.5 Electrode Impedance Measures

Electrode impedance will be measured using the standard measurement technique used in the Custom Sound programming software, as well as using an investigational measure of 4-point impedance using the CRT tool and the Freedom processor.

Conventional impedance measurements are taken between two electrodes which are also the stimulating electrodes. Stimulating through platinum electrodes induces a platinum-tissue interface impedance, which depends on the size of the electrodes and the type of stimulation used. Therefore, when traditional impedance measurements are taken, the impedance measured includes the tissue impedance as well as the interface impedance at both recording electrodes.

Four-point impedance uses recording electrodes which are different from the stimulating electrodes. This means that no interface impedance is set up at the recording electrode, and that the impedance measured is predominately the tissue impedance. Some impedance is added by the electronics of the implant and the electrodes themselves. Usually, in four-point impedance the recording electrodes are adjacent intracochlear electrodes (ICEs) and the stimulating electrodes are the two ICEs on either side of the recording electrodes. In this method, the stimulation current should flow through the tissue between the two recording electrodes, and hence the impedance measured should be the impedance of the tissue in between the recording electrodes.

Four-point impedance measurements allow the user to investigate the impedance of the tissue, without interference from the platinum-tissue interface impedance, which is typically much higher. This approach aims to provide information about the fibrous tissue growth around the electrode array with less sensitivity to variation in the impedance of individual electrodes.

7.3.6 Imaging

Where post-operative radiological imaging of the cochlea is obtained at participating centers, as part of routine clinical management, the scans will be analyzed to provide an estimate of intracochlear electrode insertion depth (angle relative to round window). Where possible, scala placement will be determined using a co-registration procedure or high resolution ConeBeam. There will not be specific imaging requirements within the CIP, however where obtained during routine clinical procedure the information will be collected and analyzed.

7.3.7 Surgical Questionnaire

The surgeon will complete the surgical questionnaire to document aspects of the surgical procedure, including but not limited to surgical approach, use of corticosteroids, and ease and depth of electrode insertion.

7.3.8 Post-Operative Cochlear Response Telemetry Recording

Post-insertion measures will be obtained using a frequency sweep (with recording from electrode 22 for signals with frequency 250, 500, 1000, and 2000 Hz delivered at a maximum comfortable listening level) and an electrode sweep (with recording using a 500 Hz acoustic signal presented at a maximum comfortable listening level and recording on electrodes 22, 20, 18, 16, 14, 12, 10, 8, 6, 4 and 2). The signal level (typically comprising a 12 ms duration stimulus and 50 ms inter-stimulus interval) will be controlled to ensure comfortable loudness presentation.

7.4 Investigational device and comparator

Comparison of endpoints are made based on subjects with and without a compromised CM response.

7.5 Subjects

7.5.1 Inclusion Criteria

- Candidate for cochlear implantation (with CI522, CI532 or Hybrid-L24 according to local indications)
- 18 years of age or older at the time of enrolment
- Pre-operative audiometric threshold in the implanted ear at 500 Hz of better than or equal to 80 dB HL
- Willingness to participate in and to comply with all requirements of the protocol

7.5.2 Exclusion Criteria

- Prior cochlear implantation in the ear to be implanted
- Ossification or any other cochlear anomaly that might prevent complete insertion of the electrode array
- Abnormal cochlear/nerve anatomy on pre-operative CT or MRI imaging (excluding a mild Mondini malformation or Large Vestibular Aqueduct Syndrome)
- Deafness due to lesions of the acoustic nerve or central auditory pathway
- Diagnosis of auditory neuropathy
- Active middle-ear infection
- Additional handicaps that would prevent participation in evaluations
- Unrealistic expectations on the part of the subject, regarding the possible benefits, risks and limitations that are inherent to the procedure and investigational device

7.6 Monitoring Plan

The study will be monitored for data quality, and adherence to ISO14155 or equivalent FDA guidelines and regulatory requirements as outlined in the study monitoring plan. Site initiation and training will be provided to ensure that study site personnel understand the protocol and schedule of activities, mechanics of the study device, study staff responsibilities, data capture and regulatory requirements. Due to the short nature of the study, Interim Monitoring activity (remote or on-site) will be completed once a site completes a multiple of 5 study subjects (i.e., after 5, 10, 15 etc. subjects are completed) or in the event of protocol compliance or GCP concerns. Completed CRT data will be collated and reviewed by the Sponsor throughout the duration of the study, to ensure that data collection is complete and consistent with the requirements of the investigation. The study close-out effort will be conducted at the conclusion of the site's participation in the study.

8 STATISTICAL CONSIDERATIONS

The primary hypothesis will be tested with a between-groups t-test or non-parametric Mann-Whitney U test using a one-sided alpha level of 0.05. This analysis will compare group mean low frequency postoperative hearing deterioration at FUV1 in the implanted ear for subjects with compromised CM compared to subjects with preserved CM. Compromised CM will be defined as a CM with an irreversible reduction in amplitude during surgery; specifically a $\geq 30\%$ reduction in maximum CM amplitude that does not recover to within 10% of the maximum amplitude. Preserved CM will be defined as a CM with $< 30\%$ amplitude reduction at any point during the surgery. Subjects not falling into the compromised or preserved CM groups will not be included in the analysis. The mean or median threshold drop for the CM compromised and CM preserved groups will be separately calculated as the mean or median of individual subjects' low frequency deterioration (4-6 week post-surgery threshold minus pre-operative threshold in the implanted ear) for the corresponding CM group. For each subject, the low frequency deterioration will be calculated as the average deterioration across the frequencies 500 Hz, 750 Hz and 1000 Hz, where there is preoperative hearing better than or equal to 80 dB HL in the implanted ear. For example, if a subject's preoperative hearing threshold is better than or equal to 80 dB HL at 500 Hz and 750 Hz but is 90 dB HL at 1 kHz, the hearing deterioration (post-operative threshold minus preoperative threshold) will be computed at 500 Hz and 750 Hz only and then averaged. It is possible that a subject could have hearing deterioration measured at 500 Hz only, if preoperative thresholds at 750 Hz and 1 kHz exceed 80 dB HL. Non-measurable post-operative thresholds will be assigned a value 1 dB above the level at which the limits of the audiometer were reached. Vibrotactile responses will not be included in the analyses.

Sample Size Estimation

Prospective sample size estimation for a two-sample t-test has been conducted, given that the study uses a between-groups design to investigate its primary hypothesis. Specifically, the planned sample size would provide 80% power at the one-tailed 0.05 alpha level to detect at least 15 dB greater deterioration in low frequency acoustic hearing threshold for subjects with compromised CM compared to preserved CM.

The following general assumptions have been made:

- A difference in mean hearing preservation of 15 dB for the compromised CM versus preserved CM groups. This difference is considered clinically meaningful, based on clinical consensus.

- An expected standard deviation of 25 dB HL. It is more conservative, but is based on the SD of 22.26 dB HL observed in low frequency hearing preservation at 3 months post-operative in the US multi-site clinical trial with 52 cochlear implant recipients using the CI422 straight electrode array (IDE G120234). This trial is considered relevant since the majority of subjects in the prospective trial will be similarly implanted with the Slim Straight array (CI522). Furthermore, in the calculation of the SD for this previous trial, low frequency hearing preservation has been calculated in the same manner as it will be in the prospective study (as the average change in threshold (post-activation minus pre-operative) across the frequencies 500 Hz, 750 Hz and 1000 Hz where there is preoperative hearing \leq 80 dB HL in the implanted ear).
- One-sided 0.05 alpha level, given that the primary endpoint is based on a directional hypothesis.
- A desired power of 0.8.

Based on the above assumptions, a minimum sample size of 36 subjects with preserved and 36 subjects with compromised CMs is required to reject a false null hypotheses of equivalent or worse hearing preservation for those subjects with preserved CM (using SigmaPlot 13.0).

This minimum sample size will be increased for the following four reasons.

- a. The sample size will be increased by 15% to 41 subjects per group to allow for the possibility that the hearing threshold data is non-normally distributed and that a nonparametric statistical analysis will be required. This 15% increase is based on what is known as the minimum asymptotic relative efficiency (ARE) of the Mann-Whitney U test relative to the paired or matched-pairs t-test. It can be proven that the ARE (or Pitman efficiency) is never less than 86.4%. When the sample size is increased by 15%, the equivalent power should be achieved, since 1.15 is approximately 1/0.864.
- b. The sample size will be increased to a total of 43 subjects per group to allow for the prediction that approximately 5% of cochlear implant recipients will not exhibit an intraoperative CM response (Dalbert et al. 2015).

Considering the following assumptions, a total sample size of 125 subjects may be required.

- c. The sample size may need to be further increased to 52 subjects, to allow for the prediction that approximately 20% of subjects will show a transient intraoperative CM drop that recovers by the end of the surgery (unpublished data, 14/1171H, Royal Victorian Eye and Ear Hospital Human Research Ethics Committee). This transient CM drop will not be categorised as a preserved CM or as a compromised CM due to uncertainty as to the likely impact of such a change on hearing preservation.
- d. The total sample size of 104 subjects (52 subjects in each group) may need to be further increased by 20%, given that the allocation of subjects to groups occurs post-implantation, and so there is no ability to control the allocation of subjects. This increase to the total sample size in anticipation of unequal groups allows for a marked difference in group size up to a ratio of 2.0, with no loss in statistical power.

Both the proportion of subjects with a transient intraoperative CM drop and the allocation of subjects in the preserved CM versus compromised CM groups are nuisance parameters not

directly related to a potential difference in outcome between the groups. Since “breaking the blind”, i.e. having access to the outcomes by CM groups, is not required to assess these parameters, modifications to the sample size may be made to the planned enrolment to ensure adequate power in the case that the assumptions outlined here (i.e. 20% of subjects show a transient CM drop, the allocation ratio between groups is different than 2.0). Such modifications do not affect the type I error rate of the study.

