10 AMENDMENTS TO THE CIP

No changes in the CIP or investigation procedures shall be effected without mutual agreement of the Principal Investigators and the Sponsor. Changes related to the scientific intent of the study shall be documented in the CIP and requires signatures from the Sponsor and the coordinating investigator. Such changes will require notification to the Ethics Committees by the Principal Investigators (and the Competent Authority by the Sponsor – if applicable). Changes relating to the investigation sites shall be documented in a separate Principal Investigator List (PIL) and referenced in the CIP.

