## 5 CHANGE HISTORY

Version	Change	Author	Date
V1	Introduction of Document	[name]	14/05/2018
V2	Additional information provided on examination of the cochlear microphonic counts after recruitment of the initial 86 subjects to determine further recruitment to ensure adequate power for examination of endpoints.	[name]	14/05/2018
V3	Two of the additional exploratory analyses removed Compromised CM definition modified Sample size justification modified to reflect change of global recruitment target from 125 to 86	[name]	06/05/2019

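### Protocol and SAP define the compromised CM group differently, the SAP rule dates from May 2019, and nothing keeps CM grouping masked to hearing outcomes

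*Protocol*

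**What the plan says.** **Grouping rule.** Protocol section 8 calls a CM compromised when its amplitude falls by at least 30% and does not recover to within 10% of maximum. It calls a CM preserved when the fall stays below 30% throughout surgery. Transient drops, predicted in about 20% of subjects, belong to neither group and are not analysed; section 4 explains this as deliberate. SAP 3.2.2 keeps the preserved definition, drops the recovery criterion and places recovered drops in the compromised group, while still using the word irreversible. The SAP change history records this under V3, dated 06/05/2019: "Compromised CM definition modified". The same version cut the recruitment target from 125 to 86.

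**Type I error.** Protocol section 8 argues that the transient share and the group split can be assessed without access to outcomes by CM group, and that enrolment may be adjusted on them: "Such modifications do not affect the type I error rate of the study". SAP 3.2.2 treats type I error control as not applicable because there is one primary endpoint.

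**Access to data.** Protocol 7.6: "Completed CRT data will be collated and reviewed by the Sponsor throughout the duration of the study". Section 9 lists the roles with EDC accounts and does not separate CM data from audiometry. The only masking stated is in 7.3.3, where the surgeon gets no CM feedback during insertion.

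**Change control.** Protocol section 10: "Changes related to the scientific intent of the study shall be documented in the CIP". The last protocol version listed is 3.0, of 23 August 2017, and it still excludes transients.

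**The concern.** The CM group is the exposure in the primary comparison and is assigned after surgery from a recorded trace. The 5% error rate therefore needs the rule, and its application to each trace, to be fixed without knowledge of the hearing results. The protocol relies on a blind of that kind but sets up no procedure for it. Neither document says who classifies traces, whether they are masked to FUV1 and FUV2 audiometry, or when the groups are locked. The Synopsis even says subjects are grouped by residual hearing at FUV1. This is probably a slip, since it conflicts with every other description, but it should be corrected.

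The rule then changed at a point when, on the planned schedule, follow-up would have been complete. The comparison that would show what moving the transients did has also gone. Protocol 7.1.4 lists ten exploratory analyses, the first comparing compromised, preserved and transient CM. SAP 3.2.4 lists eight without it, and V3 records two removals. A positive primary result could be dismissed as post hoc, and the documents would offer no answer.

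**Working it through.** **1. The plan's own figure.** Inputs from protocol section 8: "One-sided 0.05 alpha level, given that the primary endpoint is based on a directional hypothesis"; "A desired power of 0.8"; "A difference in mean hearing preservation of 15 dB for the compromised CM versus preserved CM groups"; "An expected standard deviation of 25 dB HL".

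n per group = 2 × (1.645 + 0.842)² × (25/15)² = 2 × 6.185 × 2.778 = 34.4, so 35 by the normal approximation. The t-test solution is 35.04, rounded up to 36, which is the stated figure. Then 36 × 1.15 = 41.4 (41), 41/0.95 = 43.2 (43), and 2 × 43 = 86. The figures reproduce.

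**2. Timing.** March 2017 + 17 months = about August 2018. From there to 6 May 2019 is about nine months (day/month order inferred from 14/05/2018 in the same table). The cited paper was submitted on 19 April 2019, 17 days before V3. No actual enrolment or FUV1 completion dates are given.

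**3. Enrolment changes on CM counts alone.** With no group difference, hearing change is independent of the CM counts, so the test keeps its level whatever counts trigger an extension. A simulation (40,000 null trials, extending from 86 to 125 if either group is below 36) gave 0.050. It extended in 99% of runs, so the independence argument carries more weight than the simulation. If enrolment instead stopped at 86 when significant and otherwise continued to 125, the simulated error was 0.074. The protocol's sentence is right as long as the blind holds.

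**4. Choice between the two documented rules after seeing outcomes.** Assumptions: no true difference, normal outcome, 5% without CM, 20% transient (both percentages from the protocol), and an equal split of the rest (assumed).
- Ears with a CM: 86 × 0.95 = 81.7, taken as 82. A 40/20/40 split gives 33 irreversible, 16 transient and 33 preserved.
- Protocol rule, 33 v 33: variance factor 1/33 + 1/33 = 0.0606.
- SAP rule, 49 v 33: variance factor 1/49 + 1/33 = 0.0507.
- The covariance of the two differences is also 1/49 + 1/33, because the 33 are part of the 49. Correlation = √(0.0507/0.0606) = 0.915.
- P(either statistic exceeds 1.645) = 1 − Φ₂(1.645, 1.645; 0.915) = 0.067.

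Simulations of this scenario gave 6.6% to 6.7%. Either rule fixed in advance gave about 5%. Over 10% to 30% transient, splits from 1:2 to 2:1, and N of 86 or 125 (20,000 runs each), the two-rule range was 5.8% to 7.5%.

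**5. Price of excluding transients.** 33 per group is below the 36 required. At an effect of 15/25 = 0.6, noncentrality is 0.6 × √(33/2) = 2.44 on 64 df, and power is 0.78 against 0.81 at 36 per group.

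**The case against.** The strongest case for the plan has five parts.

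- **The quoted sentence is correct.** It concerns sample size changes driven by CM counts and claims nothing about a change of grouping rule. A reader might infer that the protocol misstates its type I error; step 3 shows it does not.
- **The SAP gives a reason for the change**, a submitted paper on real-time recordings. A reader might infer from the dates that the rule was picked after looking at results. Nothing shows that anyone had seen outcomes by CM group, and the gap is measured against planned dates only. Equally, a citation alone does not show that the change was independent of this trial's data.
- **The access passages are weak evidence of unblinding.** The sponsor's review in protocol 7.6 is for completeness and consistency, and CRT files are described as stored centrally, apart from the EDC accounts. Neither shows that groups and outcomes were joined; neither is a safeguard against it.
- **Discretion is limited.** The thresholds are numerical, and the inflation is under two points in the central case. One could enlarge it by also letting transients count as preserved (simulated range 7.4% to 9.5%), but both documents rule that grouping out.
- **Part of the remedy is already planned.** SAP exploratory analysis 8 compares hearing under other CM classifications, and SAP section 1 requires deviations to be reported. Analysis 8 does not name the protocol definition, and neither provision masks or locks the classification.

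What stands is the conflict between the two rules, the absence of a masked and locked classification, and the silence on who had seen what when V3 was written.

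**Conclusion.** The point holds in a limited form. Two primary definitions coexist, the later one is dated after the planned end of follow-up, and the documents contain no procedure that would rule out outcome-informed grouping. The possible cost is a one-sided type I error of about 6.7% instead of 5%, or 5.8% to 7.5% over the splits examined. That assumes normal outcomes, the protocol's 20% transient share (varied from 10% to 30%), and a free choice of the smaller p-value from the two documented rules. It measures what is left unprotected; it does not estimate what occurred. If the grouping was in fact fixed without sight of outcomes, either rule keeps its nominal 5%, and a dated statement would largely settle the matter.

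**What to change.** 1. State one grouping rule in protocol section 8 and SAP 3.2.2. Remove the word irreversible if recovered drops are included, and correct the Synopsis sentence on grouping by FUV1 hearing.
2. Before analysis, have existing staff without access to FUV1 or FUV2 audiometry classify every trace as irreversible, transient, preserved or no CM. Put the result in a dated, locked file and only then merge it with the hearing data.
3. State in SAP 3.2.2 whether outcomes by CM status had been seen by anyone involved in the change before 06/05/2019.
4. If that cannot be excluded, test the protocol definition as primary and the V3 definition as a named sensitivity analysis. If it can, keep V3 as primary and report the protocol definition as the named sensitivity analysis.

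**Cost.** A lock step and some wording; no new subjects, measurements or staff. The four-category file supports both definitions. If the protocol definition becomes primary at 86 subjects, the analysed sample may fall to about 33 per group, with power near 0.78 on the plan's own assumptions.

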9 DATA MANAGEMENT

Source data collection is performed through DataLabs or alternative web-based system for electronic data capturing. Site personnel will be trained to use this system. Data validity has to be confirmed by the investigator through an electronic signature. An audit trail is kept by this system and data clarifications may be generated by the system and Sponsor personnel after review of data.

DataLabs or the alternative web-based system has been verified and validated by the vendor. Installation of the system within Cochlear has been validated as well. Investigation-specific implementations are validated by Data Management and consist of verification that all required items are included, validity of edit checks and appropriate functionality of conditional fields. The investigation-specific data in DataLabs can only be accessed by those that have been allocated their individual account, which are personnel of the investigational sites, Clinical Project Managers, Investigation Monitors and Data Management. Electronic data saved within the CRT system and the surgical videos will be stored in a centralized and secure location.

10 AMENDMENTS TO THE CIP

No changes in the CIP or investigation procedures shall be effected without mutual agreement of the Principal Investigators and the Sponsor. Changes related to the scientific intent of the study shall be documented in the CIP and requires signatures from the Sponsor and the coordinating investigator. Such changes will require notification to the Ethics Committees by the Principal Investigators (and the Competent Authority by the Sponsor – if applicable). Changes relating to the investigation sites shall be documented in a separate Principal Investigator List (PIL) and referenced in the CIP.

